**[name]**  
Recruiter  
The Hope Clinic  
Division of Infectious Diseases  
Department of Medicine  
Emory School of Medicine

**Rationale:** Men who have sex with men (MSM) continue to be disproportionately affected by HIV. The majority of HIV infections among MSM occur through exposure to the rectal mucosa during condomless receptive anal intercourse (CRAI). To aid in prevention, pre-exposure prophylaxis (PrEP) and post-exposure prophylaxis (PEP) are recommended for MSM who may be exposed to HIV. Current CDC recommendations for PrEP are to take the combination anti-HIV drug, tenofovir+emtricitabine (TDF/FTC), on a daily basis for the duration of someone's HIV risk exposure period, which could be months or years. For PEP, a three-drug anti-HIV medication is recommended within 72 hours of a possible exposure for a 28-day course by CDC. While PrEP and PEP are efficacious, both the daily dosing of PrEP and the 28 day course of PEP limit their utility in practice, as many users find long term adherence to these regimens to be difficult. Therefore, short course regimens taken around the time of sex (On-demand or Event-Driven PrEP; ED-PrEP) are appealing to some, and WHO endorses one such ED-PrEP regimen: two doses of TDF/FTC between 2 and 24 hours before sex, one dose 24 hours after sex, and another dose 48 hours after sex. Biomarkers (e.g. tenofovir diphosphate (TFV-DP) levels from dried blood spots) to confirm self-reported adherence to daily TDF/FTC have been an important tool used to interpret the results of PrEP clinical trials and demonstration projects. However, no such biomarkers exist to validate self-reported adherence to ED-PrEP. The aim of this study is to better understand how biomarkers might be used to validate self-reported ED-PrEP use. As ED-PrEP is intended to be used infrequently, this study will determine if the accumulation of biomarkers differs depending on whether multiple ED-PrEP dosing events are sequential or intermittent.

**Design:** To establish biomarkers to determine adherence of ED-PrEP in MSM, investigators at Emory University will collaborate with the Center for Disease Control and Prevention (CDC) to conduct a clinical trial of up to 40 MSM aged 18-59 with measurement of anti-retroviral drug concentrations in various body compartment sites. We plan to enroll participants who are HIV negative and at low risk for HIV and are not currently (or have no current plans) taking PEP or pre- exposure prophylaxis (PrEP). We will enroll participants in one of 4 study arms where they will be given the aforementioned 2-1-1 dosing of TDF/FTC.

We will recruit participants through existing research databases at the Hope Clinic and the Rollins School of Public Health, Research Match, and Clinical Data Warehouse. Internet and paper advertisements, and community venues will also be used. At the first study visit, eligibility will be determined and screening blood work (approximately 24 mL), including an HIV test, will be performed. Participants will receive doses of the drug in clinic or will provide documentation of taking doses of the drug at home. During visits, all participants will undergo blood collection (approximately 24 mL or 5 teaspoons of blood will be obtained), a urine sample, and finger stick will be collected. At certain visits, hair sampling will also be collected.

**Duration:** The duration of this study is 1 year. Participants will be considered 'on study' for no more than 24 weeks.

**Sample Size:** For this protocol we will recruit 80 HIV-negative MSM (age 18-59) who meet eligibility criteria outlined in the protocol, to ensure completion of 40 participants.

**Population:** The population to be studied in this protocol are healthy HIV negative MSM at low risk of HIV infection who currently do not desire daily PrEP and are willing to perform study procedures. We will recruit participants through existing research databases at the Hope Clinic and the Rollins School of Public Health, through internet and paper advertisements, and community venues as is currently the process for [name] ongoing research protocols.

**LAY SUMMARY:**

Men who have sex with men (MSM) continue to be disproportionately affected by HIV. In 2014, MSM made up approximately 2% of the U.S. population but accounted for 70% of the new HIV infections (CDC)(2). The majority of MSM acquire HIV after exposure to the rectal mucosa through receptive anal intercourse without condoms. Pre-exposure prophylaxis (PrEP) and post-exposure prophylaxis (PEP) are recommended for MSM who may be exposed to HIV to prevent infection. Current recommendations for PrEP are to take the combination anti-HIV drug, tenofovir+emtricitabine (TDF/FTC), on a daily basis for the duration of someone's HIV risk exposure period, which could be months or years. For PEP, a three-drug anti-HIV medication is recommended within 72 hours of a possible exposure for a 28-day course. While PrEP and PEP are effective, some people find it difficult to follow the recommended regimen. Therefore, additional short-course dosing regimens for PrEP and PEP are being implemented, such as event-driven or on-demand PrEP (ED-PrEP). This dosing regimen has patients take two doses of PrEP 2-24 hours before sex, one dose 24 hours after sex, and another dose 48 hours after sex. This proposal seeks to evaluate the usefulness of biomarkers to confirm self-reported adherence to ED-PrEP in MSM. The study drug provided in this study will not protect participants from HIV or treat any active infection.

For this protocol, we will recruit 80 HIV-negative MSM aged 18-59 in good general health. Participants will be sequentially assigned to one of 4 study arms which will determine when they will take doses of the study drug and give specimen samples. All participants will provide written informed consent at the first study visit and undergo a screening medical history and safety laboratory tests. A physical exam may also be completed. All participants will take at least 4 doses of the study drug. At study visits, participants will return to donate blood, hair, and urine samples, and a finger stick. All biologic specimens collected will be transferred to CDC on the day of collection for measurement of drug levels.

## PROJECT DESCRIPTION

**Public Health Relevance:** Event-driven PrEP (ED-PrEP) could be an effective solution for those who struggle to take a daily regimen of PrEP to prevent HIV. This is particularly important for those who engage in sexual activities less regularly, and therefore feel daily PrEP is unnecessary or too costly. However, there are currently no biomarkers available to validate self-reported ED-PrEP adherence.

**Goal:** The goal of this study is to evaluate the utility of biomarkers to validate self-reported ED-PrEP dosing.

## STUDY POPULATION

### **INCLUSION CRITERIA**

- 1) HIV-negative person, who was assigned male at birth, who reports sex with another man in the last year, and is in good general health.
- 2) Aged 18-59 years
- 3) Not currently taking PrEP and no plans to initiate during study
- 4) Not currently taking PEP
- 5) Consistent condom use and willing to use condoms for the duration of the study
- 6) Able to provide informed consent in English
- 7) No plans for relocation in the next 4 months
- 8) Willing to undergo peripheral blood, urine, finger stick, and optional hair sampling.
- 9) Willing to use study products as directed
- 10) Hepatitis B surface antigen (HBsAg) must be negative (screening lab test)
- 11) Creatinine clearance >60 ml/min

### **EXCLUSION CRITERIA**

- 1) Currently infected with hepatitis virus and/ or has liver disease
- 2) Current or chronic history of kidney disease or CrCl<60 ml/min
- 3) Continued need for, or use during the 90 days prior to enrollment, of the following medications:
  - a) Systemic immunomodulatory agents
  - b) Supraphysiologic doses of steroids (short course steroids less than 7 days duration, allowable at the discretion of the investigators)
  - c) Chemotherapy or radiation for treatment of malignancy
  - d) Experimental medications, vaccines, or biologicals
- 4) Intent to use HIV antiretroviral pre/post-exposure prophylaxis (PrEP or PEP) during the study, outside of the study procedures
- 5) Current use of hormonal therapy
- 6) Any other clinical condition or prior therapy that, in the opinion of the investigator, would make the patient unsuitable for the study or unable to comply with the study requirements.

## PROCEDURES

### Recruitment procedures

Participants will be recruited with several methods. First, the Hope Clinic maintains large databases of potential participants interested in participating in future research. Email blasts and phone calls will be made to potential participants from these databases. ResearchMatch, a secure online database used by researchers who are seeking volunteers and people who are interested in finding research/ clinical trial studies to participate in, will also be used as a recruitment source. The site will recruit from the Emory Healthcare Clinical Data Warehouse. The Clinical Data Warehouse is a repository that integrates data from clinical applications within Emory Healthcare, providing data needed for clinical reporting, research and operational support. Any contact made by email and or phone (refer to online engagement section for direct & SMS messaging script), recruiters will use one of the following scripts:

#### **Phone call**

Participants who are called will be greeted by the study staff. "Hello, my name is [      ]. I am calling from the Hope Clinic..." Staff will refer to Oral Consent and Pre-Screener.

#### **Email**

Hello my name is [      ] and I am from Emory University Hope Clinic. We are currently looking to enroll participants into a new study at the Emory University Hope Clinic. This study aims to establish biomarkers to determine adherence to on-demand PrEP which can be used to effectively prevent HIV. Study visits range from ten to twenty two visits, and you will be compensated for your time of travel and inconvenience. If you or anyone you know may be interested or have any questions about this study, please contact \_\_\_\_\_ or \_\_\_\_\_. These are the basic qualifications to participate in the study:

- You may qualify if you are:
- Age 18-59
- HIV negative man who has sex with men
- Not currently taking PrEP or PEP
- Able to consistently use condoms

Print and on-line ads will also be placed around Emory and other community settings. Finally, active recruitment will be conducted as outlined below with face-to-face and online engagements. [name] and co-investigators have a successful track record in recruiting MSM for their research protocols utilizing all of these methods.

Volunteer contact details are collected by conducting in person face-to-face and/or online social network engagement.

**Face- to-face engagements:** Participants may be actively or passively recruited at community venues listed below and engaged with limited information about the study and study qualifications. Recruiters will use 1 out of 2 generalized scripts when engaging with participants (please see section B below). A site contact sheet or a tablet using SurveyGizmo will be used to populate name, phone number, and email address of interested participants.

**A. Face -to- Face engagement**

- a. Community annual events attended by MSM (e.g. Pride festivals, MSM symposium, etc.)
- b. Bars and Night Clubs catering towards MSM
- c. Community organizations serving MSM
- d. Sporting events
- e. Other community venues where MSM might visit/patronize

**Online engagements:** Potential participants will be engaged and supplied with limited information about the study and study qualifications via paid advertisements on social media sites and dating apps. All print and online advertisement copies will be submitted to the Emory IRB for approval prior to launching these activities. Interested participants will click a posted ad with an embedded hyperlink, which will redirect them to a short screener. This screener will capture information regarding eligibility, including HIV status, name, phone number and email. Recruiters will use information obtained from online screener to contact and schedule participant visits. Potential participants may also be engaged directly on social media to assess interest in research participation. Any contact made through direct messaging, recruiters will have a generalized script (mentioned below) to follow (script can also be used for SMS contacting, as well). We will seek permission from creator/ moderator of the private website/ group, etc. before entering an interaction if possible.

**A. Online Social Network**

- f. Dating Sites (Jack'd, Adam4Adam, Grindr, etc.)
- g. Social Network (Facebook, Snapchat, Instagram, etc.)
- h. Other online social media platforms and websites where MSM might visit/patronize

**B. Script used by recruiters when engaging by direct messaging (can be used for SMS):**

- a. Hello, I am a recruiter for research studies at the Emory University Hope Clinic. We are currently looking for volunteers to participate in one or more of our HIV prevention research studies. Would you be interested in learning more?  
Thank you,  
\_\_\_\_Insert Name and contact details here\_\_\_\_

If contact responds affirmatively, then their contact information will be collected for a screening phone call (see phone screen script).

**b.** Hello, I am a recruiter for research studies at the Emory University Hope Clinic. We are currently looking for volunteers to participate in our HIV prevention research studies. All enrolled volunteers will be compensated for their time, travel, and inconvenience. Would you be interested in learning more?

Thank you,

Insert Name and contact details here

If contact responds affirmatively, then their contact information will be collected for a screening phone call (see phone screen script).

If contact responds negatively or does not respond, no further contact will be attempted.

If contact responds negatively or does not respond, no further contact will be attempted.

**c.** Hello, I am a recruiter for research studies at the Emory University Hope Clinic. We are currently looking for volunteers to participate in one of our HIV prevention research studies. All enrolled volunteers will be compensated for their time, travel, and inconvenience. To learn more, please visit

[www.hopeclinic.emory.edu/studies/enrolling-studies.html](http://www.hopeclinic.emory.edu/studies/enrolling-studies.html) or call [contact].

Thank you,

Insert Name here

If contact responds affirmatively, then their contact information will be collected for a screening phone call (see phone screen script).

If contact responds negatively or does not respond, no further contact will be attempted.

We will recruit subjects for this protocol from existing Emory University databases of MSM who have consented to be re-contacted for future research opportunities (see below).

### Study visits

When possible, study activities such as questionnaires will be done remotely due to the ongoing COVID-19 pandemic.

Eligible subjects will be sequentially assigned to study arms: A, B, C & D. Our goal is to have 10 participants complete each arm.

Participants may participate in more than one study arm; however, at least 8 weeks must lapse after completion of one study arm, before entry into another. Participants who participate in more than one arm do not have to repeat the screening visit (visit 1) when starting another arm; they will begin the new arm at visit 2. However, they will be re-consented on the consent form of the new arm prior to any arm-specific study activities being performed.

Participants who are unable to donate hair will not be considered protocol deviations.

The consent process will be conducted in a private exam room at the Hope Clinic or electronically via an online e-consent platform. Copies of the consent form for this project will not be placed in individuals' medical records since this study collects sensitive information such as HIV status and sexual orientation. All participants will be provided a copy of the signed informed consent form (ICF).

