Primary study outcome: Median (range) TFV-DP concentrations in dried blood spots will be measured at Visit 4 in Arm A and compared to TFV-DP concentrations in dried blood spots measured at Visit 16 in Arm B to compare accumulation of drug following weekly ED-PrEP dosing. In addition, TFV-DP concentrations in dried blood spots will be measured at Visit 16 in Arm C and compared to TFV-DP concentrations in dried blood spots measured at Visit 16 in Arm D to compare accumulation of drug following the different ED-PrEP dosing strategies. Differences in median drug concentrations between arms will be analyzed with a non-parametric Wilcoxon-signed rank tests and a p-value <0.05 will be considered significant.

Other drug level outcomes will be exploratory.

Future use of specimens

Leftover biologic specimens will be stored and used for future research use at Emory University Hope Clinic or the CDC. Stored samples will only be distributed to researchers who have obtained protocol approval from an IRB (or appropriate waiver).

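### The re-entry rule lets one person count on both sides of a primary comparison, the analysis plan has no rule for this, and 40 arm completions need not be 40 people

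*Combined protocol and SAP*

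**What the plan says.** The Study visits section allows re-entry: "Participants may participate in more than one study arm; however, at least 8 weeks must lapse after completion of one study arm". Re-entrants are re-consented but not re-screened; "they will begin the new arm at visit 2". No combination of arms is excluded and no maximum number of arms is set. Allocation is not random: "Eligible subjects will be sequentially assigned to study arms: A, B, C & D". The target is counted by arm: "Our goal is to have 10 participants complete each arm". Each arm's description closes enrolment at ten completers.

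The Sample Size paragraph counts people: "we will recruit 80 HIV-negative MSM (age 18-59) who meet eligibility criteria", the purpose being "to ensure completion of 40 participants". The Duration paragraph gives the study one year and caps a participant's time on study at 24 weeks, without saying whether the cap is per arm or per person.

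The Statistical Analysis Plan has two primary comparisons of TFV-DP in dried blood spots. In the first, concentrations are "measured at Visit 4 in Arm A and compared to TFV-DP concentrations in dried blood spots measured at Visit 16 in Arm B". For the second, "TFV-DP concentrations in dried blood spots will be measured at Visit 16 in Arm C and compared to TFV-DP concentrations in dried blood spots measured", the other arm being D with the same visit number. It names a Wilcoxon signed-rank test and a 0.05 threshold. It defines no pairs and does not mention a person who contributes to both arms of a comparison.

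**The concern.** A rank-sum test assumes different people in the two arms. A signed-rank test assumes that every person is in both. The re-entry rule can produce neither: some people on both sides, some on one, in a proportion known only when recruitment ends. Replacing the named test with a rank-sum test would not settle this, because the overlap comes from the enrolment rule.

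Two things are at stake. The 0.05 threshold is not the level at which the test operates once correlated values are treated as independent. And the number of people behind the results may be smaller than the Sample Size paragraph leads a reader to expect.

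**Working it through.** **The plan's own figures.** 4 arms × 10 completers = 40 and 4 arms × 20 recruited = 80, both as stated. There is no power calculation to reproduce.

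**Headcount.** Let k be the number of people shared within a comparison. With overlap only inside the two comparisons, distinct people = 40 − k(A,B) − k(C,D). This gives 40 with none shared, 30 with 5 shared in each, and 20 with 10 shared in each.

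**Does it fit in one year?**
- Arm A: 2 days from first to last dose + 28 days of follow-up = 30 days = 4.3 weeks.
- Arms B, C and D: 13 weeks + 4 weeks = 17 weeks. The 13 weeks are stated for Arm D; I assume the same for B and C from their identical visit numbering.
- Add 1 to 6 weeks from screening to Visit 2 (once only) and 8 weeks between arms.
- A then B: 4.3 + 8 + 17 + (1 to 6) = 30.3 to 35.3 weeks.
- C then D: 17 + 8 + 17 + (1 to 6) = 43 to 48 weeks.
- Shortest three-arm sequence (A plus two long arms): 4.3 + 17 + 17 + 16 + 1 = 55.3 weeks.

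Two arms fit in a year and three do not, so the floor is 40 / 2 = 20 people.

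**The 24-week cap.** One long arm with screening takes 18 to 23 weeks and fits. C and D together take 34 weeks before any gap or screening, so they cannot fit a per-person cap. A and B with screening take 22.3 to 27.3 weeks if the gap is not counted, and 30.3 to 35.3 if it is.

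**Effect on the test.** With 10 per arm, k shared and within-person correlation r, the variance of the difference in means is (2σ²/10)(1 − rk/10). The true standard error is therefore √(1 − rk/10) times the one assumed. For k = 5 this is √0.85 = 0.92 at r = 0.3, √0.70 = 0.84 at r = 0.6 and √0.60 = 0.77 at r = 0.8.

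Simulated rejection rates under no true difference follow (exact rank-sum test, two-sided 0.05, normal values, 20,000 runs per cell). The documents give neither r nor the sidedness of the test; both are assumptions.

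| Shared of 10 | r = 0.3 | r = 0.5 | r = 0.7 | r = 0.8 |
|---|---|---|---|---|
| 0 | 4.5% | 4.4% | 4.4% | 4.3% |
| 5 | 3.1% | 2.4% | 1.5% | 1.1% |
| 10 | 2.1% | 0.9% | 0.2% | 0.1% |

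A separate run gave 1.2% for 5 shared at r = 0.8. The simulation error there is √(0.011 × 0.989 / 20,000) = 0.07 percentage points, so the two agree. The signed-rank test with arbitrary pairing behaves alike: 4.9%, 2.7% and 1.1% for 0, 5 and 10 shared at r = 0.5.

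**Power of the rank-sum test that ignores overlap** (r = 0.6; 0, 5 and 10 shared):
- 0.5-SD shift: 0.16, 0.13, 0.09
- 1-SD shift: 0.51, 0.52, 0.54
- 1.5-SD shift: 0.85, 0.88, 0.93

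**Compared with keeping the pairs** (signed-rank test with each shared person paired with himself and the rest matched arbitrarily; r = 0.5, 1-SD shift): 0.62 against 0.52 with 5 shared, and 0.78 against 0.53 with 10 shared.

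**The case against.** Several points on the other side stand.

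- **Overlap is permitted, not certain.** The documents give no number of re-entrants. The floor of 20 needs every completer to do two arms, with ten of them doing two long arms over 43 to 48 of 52 weeks. It is a bound, not a forecast.
- **If the 24-week cap is per person, C then D is impossible.** The text does not say, and such a cap would largely defeat the re-entry rule. This is a reason to reconcile the two sections, not to assume that no problem exists.
- **No design ban is strictly needed.** A pre-specified analysis for partly paired data copes with the overlap and can gain from it.

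A reader might also infer more than the documents support:

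- **That shared people produce false positives.** The positive correlation makes the test conservative.
- **That the lower error rate means lost power.** This holds only for small shifts, where 10 per arm has little power anyway, or relative to an analysis that keeps the pairs.
- **That practised completers gathering in later-filled arms bias the result.** Re-entry does require completion, and Arm A is listed as closed in the Compensation section, so its completers can only move on to B, C or D. But each arm is filled to ten completers, home doses are documented in every arm, and nothing in the documents allows the effect to be sized.
- **That keeping only a shared person's first-arm value is a safe repair.** With 5 shared it leaves 10 against 5, and power at 1 SD falls from 0.52 to about 0.33 to 0.35.

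**Conclusion.** The point holds as a gap between the enrolment rule and the analysis. One person may legitimately appear in both arms of a primary comparison, and the Statistical Analysis Plan has no rule for that. With half of each arm shared and a correlation of 0.3 to 0.8, a test that ignores the overlap operates at about 3.1% down to 1.2%, against about 4.4% with separate people. The direction is conservative. The practical loss is sensitivity to small shifts and the within-person information that a suitable analysis would use. These sizes rest on assumed correlations, normal values and a two-sided exact rank-sum test.

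Completion by 40 participants is not assured; the lower bound is 20 people, given the one-year duration and 13 weeks of dosing in B and C. It should be corrected before the primary values are analysed, because deciding afterwards how to treat shared people would be a data-dependent choice.

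**What to change.** 1. **Statistical Analysis Plan, primary outcome.** Before the primary values are analysed, specify a method for partly paired data that keeps every value. One example is a mixed model on log TFV-DP with arm, period and a random person effect, with small-sample degrees of freedom. If all shared people take two arms in the same order, period is confounded with the within-person arm difference. Fitting period then gives up much of the gain from pairing, so the plan should justify the choice. **Alternatively**, for future entrants, allow re-entry only across the primary pairs (A or B to C or D, and the reverse) and use a rank-sum test. That secures separate people within each comparison, but the total could still fall to 20. People already in both arms of a pair would still need the first option.
2. **Sample Size.** Restate the target as 40 arm completions, 10 per arm. Report the number of unique people overall and the number shared within each comparison.
3. **Duration and Study visits.** Reconcile the 24-week limit with the re-entry rule by stating whether it applies per arm or per person.

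The cost is a short amendment, slightly more analysis work and a modelling assumption on the log scale or, if the bar is chosen, a smaller pool of re-entrants and no gain from within-person pairing.
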